## 4.6 PARTICIPANT WITHDRAWAL OR DISCONTINUATION

Participants are free to withdraw consent and discontinue participation in the study at any time and without prejudice to further treatment. If a participant no longer wants to receive investigational product, but is willing to come for follow-up appointments, the participant's request should be honored, if possible. The following are examples demonstrating why a participant's treatment might be discontinued.

- Toxicity precludes further study treatment.
- There is a need for any treatment not allowed by the protocol.
- The participant fails to meet the criteria for study treatment.
- Pregnancy or intent to become pregnant.
- Disease recurrence or progression.
- Investigator's discretion.

No further participant contact should be made if the participant withdraws consent for participation in the study. Information about the reason(s) for discontinuation and collection of any new or ongoing adverse events (AEs) should be collected at the time the participant withdraws consent.

For all other reasons for discontinuation from the study treatment phase, the participant should return to the clinic for the end of treatment (EOT) visit according to Section 6.8.

### 4.6.1 HANDLING PARTICIPANT WITHDRAWAL AND DISCONTINUATION

Participants enrolled in this study that withdraw prior to initiating on-study treatment will be replaced.

## 4.7 OFF-STUDY CRITERIA

Criteria that can take a participant off-study include:

- Participant requests to be withdrawn from study without further follow-up,
- Completed study follow-up period,
- Progression of disease,
- Death,
- Screen failure,
- Investigator's discretion

#### 4.7.1 SCREEN FAILURES

Any participant that has signed the consent form (for either screening or study participation) but does not meet the study eligibility criteria, or meets study eligibility criteria but terminates their participation prior to receiving study treatment, will be considered a screen failure. The reason for screen failure should be captured in the database for each participant failing to meet the eligibility criteria.

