### 6.3.1 SCREEN FAILURES

A participant who signed an informed consent form but does not initiate planned SBRT, for any reason, will be considered a screen failure. Those found not to be eligible after signing the study consent will be considered screening failures, and data will be handled in the same manner. The demographic information, informed consent, and inclusion/exclusion pages must also be completed for screen failures. No other data except reason for screen failure will be entered into the clinical database for individuals who are screen failures.

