### **9.3 SAMPLE SIZE, POWER, ACCRUAL RATE AND STUDY DURATION**

#### **9.3.1 SAMPLE SIZE AND POWER**

The primary goal of this pilot study is to help identify unforeseen problems with a subsequent larger-scale clinical trial. We predict that there is a 20% probability that a particular patient's treatment plan will fail to meet all dosimetric constraints, most notably the 700 cc critical volume constraint for the liver minus GTV since many cirrhotic patients have small total liver volumes, rendering them ineligible for SBRT. A sample size of 15 patients will ensure that we will encounter at least one incidence of SBRT ineligibility at a 95% CI.

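### The pilot's only success proportion is conditional on SBRT being delivered, and delivery among eligible participants is never estimated

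*Combined protocol and SAP*

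**What the plan says.** Three sections of the combined protocol and SAP decide what happens to someone who signs consent and never receives a fraction.

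- Section 4.7.1 covers people who fail eligibility and also anyone who "meets study eligibility criteria but terminates their participation prior to receiving study treatment, will be considered a screen failure". Its last sentence asks for a reason only for those who fail the criteria.
- Section 6.3.1 is broader: "A participant who signed an informed consent form but does not initiate planned SBRT, for any reason, will be considered a screen failure". Demographic, consent and inclusion/exclusion pages are completed, and then "No other data except reason for screen failure will be entered into the clinical database for individuals who are screen failures".
- Section 4.6.1 adds: "Participants enrolled in this study that withdraw prior to initiating on-study treatment will be replaced".

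Section 9.1 limits the efficacy set to participants with 85% or more of the prescribed dose, and section 9.2.2 computes the primary proportion in that set with an exact 95% interval. The safety set starts at the first fraction. Neither the endpoint lists (3.2.1 to 3.2.3) nor the analyses (9.2.2 to 9.2.4) include the number or proportion of eligible participants who start or complete SBRT.

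On purpose, section 9.3.1 states: "The primary goal of this pilot study is to help identify unforeseen problems with a subsequent larger-scale clinical trial". Section 1.3 says the pilot should reveal obstacles to taking part in a later trial and estimate bridging against historical controls.

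**The concern.** Two different groups share one label. A person whose plan cannot meet the dose constraints is ineligible under inclusion criterion 7. A person who meets every criterion but never reaches fraction 1 is a delivery failure, or occasionally an early transplant. The plan leaves room for the second group: screening lasts up to 28 days (4.5), extra visits are scheduled while insurance authorisation is sought (6.3), and fiducial placement, where needed, falls within screening (6.8).

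Whether eligible patients with Child-Pugh B8 or worse can be brought to treatment is a natural part of a feasibility question, and the team designing the larger trial will need the figure. Followed as written, the report would give success among the treated and say nothing about how many eligible people were lost beforehand. The comparison with historical controls is affected too. Section 1.1 quotes progression beyond Milan in 20-30% of listed patients, and a proportion restricted to people who received nearly all their SBRT does not describe the same kind of population.

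**Working it through.** **1. The plan's own figure.** Section 9.3.1 assumes a 20% chance that a patient's plan fails the constraints and concludes: "A sample size of 15 patients will ensure that we will encounter at least one incidence of SBRT ineligibility at a 95% CI". The smallest n with 1 − 0.80ⁿ ≥ 0.95 is ln(0.05)/ln(0.80) = 13.43, so 14. With 15, 1 − 0.80¹⁵ = 0.965. The stated 15 is adequate for that aim. It concerns dosimetric ineligibility only; eligible participants who do not start play no part in it. The text also does not say whether the 15 are consented or treated. If 15 must be treated, 15/0.80 = 18.75, so about 19 consented would be needed for dosimetric losses alone.

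**2. Path of an eligible non-starter.**
- 4.7.1 and 6.3.1: classed as a screen failure.
- 4.6.1: replaced, if the reason is withdrawal. The section does not mention other reasons.
- 9.1 and 9.2.2: dose received is 0%, below 85%, so outside the primary denominator whatever the label.
- 9.2.3 and 9.2.4: in no planned summary of delivery.

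The dose rule is what keeps non-starters out of the primary proportion. The label and the replacement rule keep them from being reported as a group of their own.

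**3. Size, with assumed counts.** Let s of 15 treated and analysed participants succeed, let k eligible participants not start, and let u of those k succeed anyway.

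- Planned report: s/15.
- Over all eligible: (s + u)/(15 + k).
- Starting proportion: 15/(15 + k).

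The documents give no value for s, k or u. With s = 12, and exact (Clopper-Pearson) 95% intervals in brackets:

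| k | Start SBRT | Non-starters not bridged (u = 0) | All non-starters succeed (u = k) |
|---|---|---|---|
| 0 | 15/15 = 100% (78.2-100) | 12/15 = 80.0% (51.9-95.7) | 80.0% |
| 1 | 15/16 = 93.8% (69.8-99.8) | 12/16 = 75.0% (47.6-92.7) | 13/16 = 81.3% |
| 2 | 15/17 = 88.2% (63.6-98.5) | 12/17 = 70.6% (44.0-89.7) | 14/17 = 82.4% |
| 3 | 15/18 = 83.3% (58.6-96.4) | 12/18 = 66.7% (41.0-86.7) | 15/18 = 83.3% |
| 5 | 15/20 = 75.0% (50.9-91.3) | 12/20 = 60.0% (36.1-80.9) | 17/20 = 85.0% |

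With u = 0 the planned figure is multiplied by 15/(15 + k). From s = 9, 60.0% becomes 9/18 = 50.0% at k = 3.

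**4. Direction.** (s + u)/(15 + k) is below s/15 exactly when u/k is below s/15, that is, when non-starters do worse than the treated. For s = 12 and k = 3, u = 0, 1, 2, 3 gives 66.7%, 72.2%, 77.8% and 83.3%, against 80.0%.

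**The case against.** A reader might infer that the screen-failure label and the replacement rule erase non-delivery by definition and make the success proportion too high. The documents do not support that.

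- **Cause.** The 85% rule in 9.1 excludes non-starters by itself. Rewriting 4.7.1, 6.3.1 and 4.6.1 alone would leave the primary figure unchanged.
- **Recoverability.** Section 6.3.1 provides for a reason for anyone who does not start and keeps the inclusion/exclusion pages, and 4.4.1 registers everyone who consents. Eligible non-starters can be counted. What is missing is a planned report and consistent wording, since 4.7.1 asks for a reason from a narrower group.
- **Bias.** Sections 3.2.1 and 9.2.2 start the clock at SBRT, so the quantity defined is a proportion among treated people. Omitting people with no time zero does not bias it.
- **Direction.** The Milan criteria in 7.5 concern tumour size, number and spread, not liver function. A non-starter could still meet them, and one transplanted before SBRT has been bridged. That early attrition falls on the sickest patients is plausible but nowhere documented.
- **Consequence.** The synopsis states that there is no formal hypothesis test, and no success threshold is set, so no decision rule would be crossed.

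It can also be said that section 2.1 defines feasibility as disease control sufficient for transplant eligibility, which makes uptake a matter of taste. That defends the choice of primary endpoint. It does not explain why a pilot that says it is looking for unforeseen problems and barriers leaves delivery among eligible patients out of its report.

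**Conclusion.** The point holds as a gap in what is estimated; it is not an error in the primary analysis. The trial will report one success proportion, conditional on delivery, and will not estimate delivery among eligible participants, although the data for a count will largely exist.

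The size cannot be derived from the documents. Under the assumed 12/15, three eligible non-starters move the all-eligible figure to anywhere from 67% to 83%, depending on how they fare. The starting proportion itself would be 83% with an exact interval of 59% to 96%. Even with no non-starters in 15, the lower limit would be 78%, so the pilot can describe delivery only coarsely. That is still more than the plan offers now. The change is a worthwhile, low-cost improvement, and nothing in it calls for abandoning the treated-only estimate.

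**What to change.** 1. In 4.7.1 and 6.3.1, separate ineligible participants (including dosimetric failures under inclusion criterion 7) from eligible participants in whom SBRT was not started. Align the two sections so that a reason is recorded for both groups.
2. In 9.2, report among eligible consented participants the proportion who start SBRT and the proportion who reach 85% of the prescribed dose, each with an exact 95% interval.
3. Keep the primary analysis. Add a sensitivity analysis over all eligible participants in which non-starters count as not bridged, with any transplanted before SBRT shown separately. State in advance how those who start but stay below 85% are counted.
4. Amend the data-entry limit in 6.3.1 so that transplant and vital status can be recorded for eligible non-starters, but only where consent permits: section 4.6 rules out contact after consent is withdrawn. The analysis in item 3 can be run without these data; they help to show which way the difference goes.
5. State in 9.3.1 whether the 15 are consented or treated.

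The cost is protocol and consent wording, one CRF category, two status items, two proportions and one sensitivity analysis. No participants are added and treatment is unchanged. The downsides are a possibly less favourable feasibility figure and incomplete status data on those who withdraw consent.

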#### 4.8 STUDY DISCONTINUATION

This study may be temporarily suspended or prematurely terminated if there is sufficient reasonable cause. Written notification, documenting the reason for study suspension or termination, will be provided by the suspending or terminating party to IRB and other regulatory authorities (as applicable). If the study is prematurely terminated or suspended, the Investigator will promptly inform the IRB and will provide the reason(s) for the termination or suspension.

Reasons for terminating the study may include the following:

- Incidence or severity of adverse events, in this or other studies, indicates a potential health hazard to participants.
- Data that are not sufficiently complete and/or evaluable.
- Investigator(s) do not adhere to the study protocol, or applicable regulatory guidelines in conducting the study.
- Participant enrollment is unsatisfactory.
- Submission of knowingly false information from the study site to regulatory authorities.
- Upon instruction by local or other regulatory, or oversight authority.

Study may resume once concerns about safety, protocol compliance, data quality are addressed and satisfy the Sponsor, IRB and/or other regulatory authority (e.g. FDA).

## 5. TREATMENT PLAN

### 5.1 DOSAGE AND ADMINISTRATION

On-study treatment will be administered on an out-patient basis. Reported adverse events and potential risks are described in Section 8.4. Appropriate dose modifications are described in Section 5.2, Dose modifications. No investigational or commercial agents or therapies other than those described below may be administered with the intent to treat the participant's malignancy.

#### 5.1.1 SIMULATION

All imaging for radiation planning will be performed according to institutional guidelines. If deemed necessary by the treating radiation oncologist for targeting purposes, eligible participants will undergo placement of intrahepatic fiducial markers prior to simulation (refer to Section 6.1.7). Imaging for radiation planning will include triple-phase contrast-enhanced simulation with immobilization. Participants will be immobilized with standard motion management techniques. The simulation should be performed with the participant in treatment position (i.e., supine, with arms above head).

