## 4. STUDY ENROLLMENT AND WITHDRAWAL

### 4.1 PARTICIPANT INCLUSION CRITERIA

To be eligible to participate in this study, an individual must meet all of the following criteria:

1. Ability to understand and the willingness to sign a written informed consent document.
2. Age  $\geq 18$  years at time of informed consent. All people regardless of biologic sex and members of all races and ethnic groups will be included.
3. Must be listed or recommended to be listed for orthotopic liver transplantation at the participating institution
4. Have a CP score  $\geq B8$ , as defined in Appendix A
5. Eastern Clinical Oncology Group (ECOG) performance status  $\leq 2$ , or Karnofsky Performance Scale  $>60$  (refer to Appendix B)
6. Must have a life expectancy  $> 12$  weeks
7. Safe radiation treatment planning parameters that adhere to all organs at risk constraints per section 5.1 of the protocol. If normal organs at risk constraints (including at least 700cc of uninvolved liver) are unable to be met at the lowest dose modification (30 Gy in 5 fractions), the patient is deemed ineligible for SBRT and deemed a screen failure.
8. Except for prior radiotherapy or radioembolization, other prior therapies to previously treated lesions, are permitted.
9. People of childbearing potential must have a negative urine or serum pregnancy test within 72 hours prior to receiving the first dose of SBRT. If the urine test is positive or cannot be confirmed as negative, a serum pregnancy test will be required.

Participants of childbearing potential are those who have not been surgically sterilized or have not been free from menses for  $>1$  year without an alternative medical cause.

*Note: Abstinence is acceptable if this is the preferred contraception for the participant.*

10. No other prior invasive malignancy is allowed except for the following: adequately treated basal (or squamous cell) skin cancer, in situ breast or cervical cancer. Stage I or II invasive cancer treated with a curative intent without evidence of disease recurrence for at least five years.

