#### 5.1.2 TARGET AND NORMAL STRUCTURE CONTOURING

Diagnostic CT scans and MRIs (if available) will be fused to the CT simulation for contouring purposes to help guide contouring of target and normal structures, which will be recorded on the CT images. Normal structures to be contoured include spinal cord, esophagus, heart, chest wall, body, stomach, duodenum, small bowel, large bowel, lung, liver, and kidneys.

The gross tumor volume (GTV) (or internal target volume (ITV) if 4-dimensional CT is utilized) will be contoured using all available images, and the planning target volume (PTV) will be constructed using a 5 mm circumferential margin. All participants must have a critical volume of liver minus GTV (or ITV) of at least 700 cm^3.

If tumor motion is greater than 3 mm, participants will be simulated and treated with a breathhold technique. In breathhold technique, the participant is treated in a specific inspiratory phase of the respiratory cycle. If appropriate and at the discretion of the treating physician, participants may also undergo a MRI simulation in the treatment position to assist in the contouring of tumor and normal structure. If performed, MRI should be done with contrast.

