## 6.8 SCHEDULE OF EVENTS

Visit Days	Screening	Treatment					Follow-Up B (±4 weeks)	
	Days -28 to -1	Days † (+7 days)						
		1	3	5	7	9*		
SBRT A		X	X	X	X	X		
Informed consent	X							
Inclusion/exclusion criteria	X							
Medical history	X						X B	
Prior/concomitant medications	X						X B	
Physical Examination C	X						X B	
Radiographic Imaging	X	X D	X D	X D	X D	X D	X E	
Hematology F	X						X B	
Biochemistry G	X						X B	
Coagulation	X						X	
Pregnancy test	X							
Fiducial placement (if needed)	X							
AE assessment	X	X					X	
EORTC QLQ-30	X						X B	
FACT-Hep	X						X B	

† Starting on day 1, SBRT dose fractions are given every other day (i.e., Monday-Friday), but not administered on Saturdays, Sundays, or holidays. Dosing interruptions because of weekends and holidays will be recorded in CRF.

\*Day 9 study assessments of radiographic imaging and AE collection will serve as Early Termination and/or End of Treatment Visit.

A Scheduled SBRT visits may be delayed by no more than 7 days between each visit, or may occur earlier than scheduled by no more than 3 days.

B Follow-up assessment to occur 6 weeks following completion of SBRT then every 3 months up to 2 years post SBRT therapy

C All physical exams will include assessing weight, vital signs, and ECOG performance status. Height will be measured at screening visit only.

DCone-beam CT will be obtained prior to each SBRT fraction.

E Participants will undergo surveillance imaging (e.g., CT scan) 6 weeks following completion of SBRT and then every 3 months for the first 2 years.

F Hemoglobin, platelets and white cell count with differential white count

G Biochemistry to include renal (creatinine, urea, sodium, potassium) and liver function (AST, ALT, bilirubin)

HAEs and laboratory safety measurements will be graded per NCI CTCAE version 5.0 as well as definition of radiation-induced liver disease (Child-Pugh elevation of 2 or more). All AEs, whether gradable by CTCAE or not, will also be evaluated for seriousness. Record all AEs and SAEs occurring from the time of consent signing to 3 months following the completion of SBRT.

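### Where fiducial markers are used, they go in before the plan that decides inclusion 7 exists, so some patients may have a liver procedure and then be screened out, and the protocol keeps no count of them

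*Combined protocol and SAP*

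**What the plan says.** Section 5.1.1 (Simulation) makes marker placement conditional and puts it before simulation: where the treating radiation oncologist judges markers necessary, "eligible participants will undergo placement of intrahepatic fiducial markers prior to simulation". The Schedule of Events (6.8) lists placement in the screening column, again only if needed, and section 6.1.7 allows that some tumors can be targeted without markers.

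Inclusion criterion 7 in section 4.1 requires "Safe radiation treatment planning parameters that adhere to all organs at risk constraints per section 5.1 of the protocol". Under sections 4.1 and 5.1.3, a patient whose plan cannot meet the constraints even at the lowest dose level is ineligible and a screen failure.

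Section 5.1.2 has the liver and tumor contoured on the CT simulation, with diagnostic scans fused to it. It also sets a requirement on volume alone: "All participants must have a critical volume of liver minus GTV (or ITV) of at least 700" cm³. Table 3 (section 5.1.4) uses the same 700 cc of liver minus GTV but pairs it with a dose limit of 15 Gy.

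Section 9.3.1 predicts that "there is a 20% probability that a particular patient's treatment plan will fail to meet all dosimetric constraints", and names the 700 cc liver constraint as the leading cause "since many cirrhotic patients have small total liver volumes, rendering them ineligible for SBRT".

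Section 6.3.1 limits what is entered for a screen failure to demographics, consent, the eligibility pages and the reason for failure.

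**The concern.** Section 5.1.1 reserves markers for patients who are already eligible. One eligibility criterion depends on a plan that does not exist until after simulation, so no patient can be known to satisfy it when the markers are placed. The protocol expects this criterion to fail in one patient in five, and its sample size is chosen so that such patients will be met.

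Two things are at stake. First, a patient with Child-Pugh B8 or worse cirrhosis may have antithrombotic drugs held (section 6.1.7) and markers placed in the liver, and then be refused the treatment that the markers were for. Second, the study would not show how often this happens. Section 6.3.1 enters nothing about marker placement in screen failures, section 6.3 leaves toxicities before treatment out of the analysis, and the safety set in section 9.1 starts at the first fraction. Section 6.1.6 asks for adverse events to be recorded from consent, which does not sit easily with section 6.3.1. A pilot whose declared purpose is to uncover problems for a larger trial should be able to report this one.

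**Working it through.** **Inputs.** Plan-failure probability p = 0.20 and N = 15 (section 9.3.1). The share of patients needing markers, f, is not given. It is an assumption, shown here from 0.10 to 1.00. Section 9.3.1 ties the 20% to ineligibility, so it is read as failure after dose de-escalation.

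**1. The plan's own figure.** Section 9.3.1 states: "A sample size of 15 patients will ensure that we will encounter at least one incidence of SBRT ineligibility at a 95% CI". Reading this as a 95% probability of at least one case:

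n = ln(1 − 0.95) / ln(1 − 0.20) = 13.43, rounded up to 14.

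At n = 14 the probability is 1 − 0.80^14 = 95.6%. At n = 15 it is 1 − 0.80^15 = 96.5%. The stated 15 is consistent with p = 0.20.

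**2. Order of steps.** Markers if needed (5.1.1, 6.8) → simulation (5.1.1) → contouring on the simulation CT (5.1.2) → plan tested at 40, 35 and 30 Gy (5.1.3) → criterion 7 decided (4.1). Placement precedes the decision.

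**3. Expected number implanted and then excluded.** If marker need and plan failure are independent, each planned patient has probability 0.20 × f of both.

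- Per 15 planned: expected = 15 × 0.20 × f = 3 × f, and P(at least one) = 1 − (1 − 0.20f)^15.
- Per 15 treated: expected number planned = 15 / 0.80 = 18.75, expected count = 18.75 × 0.20 × f = 3.75 × f, and P(at least one) = 1 − [0.80 / (0.80 + 0.20f)]^15.

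| f (assumed) | Expected, 15 planned | P(at least one) | Expected, 15 treated | P(at least one) |
|---|---|---|---|---|
| 0.10 | 0.3 | 26% | 0.375 | 31% |
| 0.25 | 0.75 | 54% | 0.94 | 60% |
| 0.50 | 1.5 | 79% | 1.9 | 83% |
| 1.00 | 3.0 | 96% | 3.75 | 96% |

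**4. Dependence.** Without independence, the joint probability lies between max(0, f + 0.20 − 1) and min(f, 0.20). Per 15 planned, f = 0.10 gives 0 to 15 × 0.10 = 1.5 patients, and f = 0.25 or 0.50 gives 0 to 15 × 0.20 = 3.0. At f = 1.00 it is 3.0 whatever the dependence.

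**5. What could be seen before placement.** There are two kinds of failure.

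- Liver minus GTV below the 700 cm³ floor in section 5.1.2. This fails at every dose level, and it can be estimated on the CT or MRI already scheduled at screening. An ITV is at least as large as the GTV, so using the ITV leaves no more liver.
- Liver above the floor, but a dose-based constraint in Table 3 is missed. This needs a plan.

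The documents do not divide the 20% between the two. The share that a volume estimate could reveal is anywhere from 0% to 100%.

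**The case against.** The strongest reply is that placement is neither routine nor unguarded. It is at the treating radiation oncologist's discretion, section 6.1.7 accepts that some tumors need no markers, and exclusion 4 (section 4.2) bars patients whose coagulopathy makes placement unsafe. A clinician with the screening scans in hand may well look at liver volume first. All of this stands, and it is why the result has to be stated as 3 × f with f unknown. None of it settles criterion 7, and no section requires a volume or dosimetric check before placement. The multidisciplinary review of criteria in section 4.3 is optional and cannot judge a plan not yet made.

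A reader might go further in four ways that the documents do not support.

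- That 20% of all participants will be implanted and excluded. This holds only if f = 1.
- That an early volume check would prevent most of these cases. Table 3 attaches 15 Gy to the 700 cc, and section 5.1.3 lowers the dose when constraints are missed, so passing can depend on dose. Nothing supports a lower bound above 0% on the share caught.
- That the figures measure harm. The documents give no complication rate for marker placement.
- That the primary result is biased. The efficacy set (section 9.1) requires at least 85% of the prescribed dose, so screen failures never enter it.

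**Conclusion.** The point holds as an inconsistency of moderate severity, not as a fault that must be cured before the study can proceed. The eligibility wording in section 5.1.1 cannot be true for inclusion criterion 7. At the protocol's own failure rate, between 0.3 and 3.0 patients per 15 planned would be expected to receive markers and then be screened out as f runs from 0.10 to 1.00, with a 26% to 96% chance of at least one. If the 15 are counted as treated, the range is 0.375 to 3.75.

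This rests on three things: the 20% in section 9.3.1, an assumed f, and independence of marker need and plan failure. How many cases could be avoided is unknown, because the split between absolute-volume and dose-based failures is not given. The gap in recording depends on none of these assumptions: under section 6.3.1 as written, such patients would not be identifiable in the clinical database.

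**What to change.** 1. Reconcile section 4.1 item 7 with sections 5.1.1, 5.1.2, 6.3 and 6.8. The text should state which eligibility criteria must be met before marker placement, and at what point the protocol's existing 700 cm³ requirement is first assessed. The clinical rule itself is for the sponsor to decide.
2. Amend section 6.3.1 so that marker placement is recorded for screen failures, and report the number of participants who had markers placed and then failed planning as a feasibility result, beside the number planned and the number with markers. This would also supply the missing f for the larger trial. In the same edit, bring section 6.3.1 into line with the recording of adverse events from consent in section 6.1.6.

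The cost is amendment wording, one extra data item and, if the sponsor chooses to estimate volume on the screening scan, a little contouring. The limitation is that borderline volumes and dose-based failures would still be found only after simulation.
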